7.8.3 Analysis of Secondary and Exploratory Endpoints

For the purposes of analyzing the association between percent change from baseline in intratumoral peak lactate/pyruvate ratio on HP MRI with subsequent clinical outcomes, the cohort will be dichotomized by the median percent change. The objective response rate by RECIST 1.1 criteria and clinical benefit rate (response or stable disease for > 24 weeks) will be compared between dichotomized groups using the chi-squared test. The log rank test will be used to compare the radiographic progression-free survival between the two groups.

Safety analyses will be performed for all patients having received a dose of HP C-13 pyruvate. The study will use the NCI CTCAE v4.0.

Analyses will be performed to compare the HP MR markers with immunohistochemical and enzyme expression and activity data from biopsy tissue to investigate the molecular and physiological underpinnings of the HP ¹³C MR data. When both the HP biomarker and molecular biomarker (LDHA activity) are continuous variables, Spearman's rank correlation coefficient will be used to investigate a possible correlation between them. If the outcome is categorical (e.g. immunohistochemistry score 0-1+ vs 2-3+ for pS6, pAkt, LDHA, and MCT 1/4 expression), the HP biomarker distributions will be compared between the two categories using the Mann-Whitney test.

Intra-patient reproducibility of HP lac/pyr ratio for patients who undergo repeated dose imaging studies will be descriptively reported using summary statistics (mean difference, standard deviation, range).

No adjustment will be made for multiple comparisons for the analysis of the secondary and exploratory endpoints.

8 Study Management

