2.2 Secondary Objectives

- To investigate for an association between percent change from baseline in peak intratumoral hyperpolarized lactate to pyruvate ratio after initiation of treatment with PI3K/mTOR pathway inhibitor with subsequent clinical outcomes including objective response rate, clinical benefit rate, and progression-free survival. (Part B)
- To characterize further the safety profile of hyperpolarized C-13 pyruvateinjection
- To determine the reproducibility of intra-tumoral HP lac/pyr ratio with same-day repeated dose studies.

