5.4 Initiation of PI3K/mTOR Pathway-Directed Therapy (Part B Only)

Patients enrolled in Part B will subsequently begin treatment with systemic therapy directed towards the PI3K/mTOR pathway following completion of baseline/screening procedures. Treatment may be given as standard of care with commercial supply (e.g. everolimus) or via participation on therapeutic clinical trial. The study procedures for patients enrolled on a therapeutic trial take precedent over the procedures outlined in the current protocol.

5.5 Day 21 (+/- 14 day) Metabolic MR/HP C-13 Pyruvate study (Part B Only)

Patients will undergo repeat MR scan as per above procedures after 21 days (+/- 14 days) of treatment with androgen signaling inhibitor. Where applicable, patients should take the PI3K/mTOR pathway inhibitor on the day of the MR scan. The target lesion to be evaluated by metabolic MRI will be the same as the prior MR unless lesion has become inevaluable in the interim in the judgment of study investigators. In these cases, an alternate lesion (evaluable baseline MR whenever possible, and adjacent to original target lesion) will be selected for analysis.

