7.1 Image Processing and Analysis

For each patient, a target metastatic lesion will be selected on the basis of standard imaging (CT or MRI). A region-of-interest (ROI) will be manually drawn in the target lesion, and the same lesion will be evaluated on serial MR scans if the lesion continues to remain evaluable by MRI. If lesion is no longer evaluable on follow up scan, an alternative lesion will be selected on the basis of proximity to original lesion and accessibility by radiofrequency coil for purposes of metabolic MR evaluation.

For the analysis and interpretation of the HP ¹³C MR imaging data, we will utilize the opensource DICOM software package (SIVIC) to align, display and quantitatively interrogate serial multiparametric imaging data. Intra-tumoral ROI will be used to quantify peak HP lactate/pyruvate ratio values in the selected volumes of interest.

In an exploratory fashion, additional metastatic sites in addition to the target lesion will be analyzed and interpreted to determine intra-tumoral peak HP lactate/pyruvate ratio.

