7.2 Study Endpoints

Primary endpoints:

Part A: Signal-to-noise ratio with respect to intra-tumoral hyperpolarized C-13 lac/pyr ratio detected within target liver or other intraabdominal metastasis in patients with advanced solid tumor malignancies.

Part B: Mean percent change from baseline in peak intra-tumoral hyperpolarized lactate/pyruvate ratio after initiation of treatment with PI3K/mTOR pathway inhibitor.

Secondary endpoints

- Frequency of adverse events as graded by Common Toxicity Criteria version 4.0
- Association between percent change from baseline in peak intra-tumoral HP lactate/pyruvate ratio on metabolic MR imaging with subsequent outcomes on PI3K/mTOR pathway inhibitor therapy including clinical benefit rate and progression-free survival (Part B)
- Intra-patient reproducibility of HP lac/pyr ratio for patients who undergo repeated dose imaging studies, as descriptively reported using summary statistics (mean difference, standard deviation, range).

Exploratory endpoint

Association between HP peak lactate/pyruvate signal with immunohistochemical expression level of markers of PI3K/mTOR and glycolytic pathway, including LDH, phosphorylated S6, and phosphorylated Akt. (Part B)

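### Percent change in lactate/pyruvate ratio is tested against response, clinical benefit and PFS only after a sample-median split, which misses a graded association more often than a rank analysis would

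*Combined protocol and SAP*

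**What the plan says.** Section 2.2 sets the secondary objective: "To investigate for an association between percent change from baseline in peak intratumoral hyperpolarized lactate to pyruvate ratio" and response rate, clinical benefit rate and PFS. Section 7.2 words the endpoint in the same way: "Association between percent change from baseline in peak intra-tumoral HP lactate/pyruvate ratio on metabolic MR imaging with subsequent outcomes". Neither names a threshold.

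Section 7.8.3 supplies the analysis: "the cohort will be dichotomized by the median percent change". Response and clinical benefit are then compared between the two halves by chi-squared. For PFS, "The log rank test will be used to compare the radiographic progression-free survival between the two groups". No reason is given for the cut, and nothing else in the document relates the undivided change to these outcomes.

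For the tissue markers, the same section leaves the imaging biomarker whole. With a continuous marker, Spearman's "rank correlation coefficient will be used to investigate a possible correlation between them". With a two-category marker, "the HP biomarker distributions will be compared between the two categories using the Mann-Whitney test".

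**The concern.** After a median split, a patient just past the median counts the same as the patient with the largest decline. If outcome improves steadily with the size of the decline, the test ignores most of that gradient. The analysis also gives no estimate of how outcome varies with the size of the change, and the cut is a feature of this sample rather than a threshold another study could use.

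This is the plan's only analysis linking imaging change to patient outcome, and Section 1.1 looks ahead to using the scan as a surrogate for tumour response. With 30 patients there is little information to spare. Response (yes or no) against percent change has the same structure as a two-category tissue marker against the imaging biomarker, for which the plan already chooses a rank test.

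**Working it through.** **Inputs from the plan.** 30 evaluable patients in Part B (Section 7.3); a split at the sample median, so 15 v 15 if all are evaluable (7.8.3); follow-up averaging about 6 months (3.4). The only power figure in the document, above 85% in Section 7.3, is for the primary paired t-test. It comes without an SD and does not bear on this analysis, so there is no stated figure to reproduce.

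**Assumptions.** Two-sided 5%. Change normally distributed. Exponential PFS with a 6-month median at the mean change. Censoring uniform over 6 to 30 months, plus exponential drop-out with mean 30 months. This gives about 20 events and a mean follow-up of 6.0 months. No drop-out gives about 24 events; drop-out with mean 13 months gives about 17. Effects per SD and outcome rates are assumed. Each setting has 40,000 simulated trials, so the Monte Carlo standard error is at most √(0.25/40,000) = 0.25 points.

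**Tests.** For PFS, the Cox score test rejects if U²/V > 3.84, where U = Σ(z − z̄) over events, z̄ is the mean of z among those at risk, and V is the matching sum of risk-set variances. With z = 0/1 by median this is the log-rank test; with z = rank it is the alternative. For binary outcomes, chi-squared on the split is compared with Mann-Whitney on the undivided change.

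**Power (%):**

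| Setting, n = 30 | Split | Rank | Difference |
|---|---|---|---|
| PFS, HR 1.0 (type I error) | 5.6 | 5.6 | 0.0 |
| PFS, HR 1.25 | 12.1 | 15.6 | +3.5 |
| PFS, HR 1.5 | 27.0 | 37.4 | +10.4 |
| PFS, HR 1.75, about 20 events | 43.1 | 59.9 | +16.8 |
| PFS, HR 1.75, about 17 events | 37.1 | 51.7 | +14.6 |
| PFS, HR 1.75, about 24 events | 49.5 | 67.0 | +17.5 |
| PFS, HR 1.75, extra log-hazard SD 0.7 | 32.2 | 45.4 | +13.2 |
| PFS, HR 1.75, extra log-hazard SD 1.0 | 26.3 | 36.6 | +10.3 |
| Clinical benefit, 40% rate, OR 2 | 26.6 | 36.7 | +10.1 |
| Clinical benefit, 40% rate, OR 3 | 51.2 | 68.0 | +16.8 |
| Response, 20% rate, OR 2 | 19.3 | 26.2 | +6.9 |
| Response, 20% rate, OR 3 | 35.5 | 51.0 | +15.5 |
| PFS, step HR 3 at population median | 51.8 | 50.5 | −1.3 |
| PFS, step HR 3 at this sample's median | 66.3 | 52.9 | −13.4 |

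PFS rows without an event count use the 30-month drop-out. The extra log-hazard rows stand for the mix of tumour types and agents that Section 3.1 admits. Type I error for the binary tests is 4.8% to 5.0% (split) and 4.6% to 4.8% (rank). A continuity-corrected Mann-Whitney test gives 49% in place of 51% for response at OR 3.

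A separate simulation with a different censoring model (0%, 20% or 40% censored) also put rank ahead in every graded setting, by about 9 to 19 points for PFS (HR 1.5 to 2.5) and 6 to 19 for binary outcomes (rates 10% to 50%, OR 2 to 4).

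**Information lost by the split.** Against a correctly specified linear analysis the loss is 1 − corr(change, split)²: 36% if normal (1 − 2/π), 25% if uniform, 50% if Laplace, 52% if exponential (1 − (ln 2)²). Ranks lose some information too, so the recoverable part is smaller: 33% if normal (1 − (2/π)/(3/π)), 25%, 41% and 36% respectively.

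**Why ranks and not the raw change.** Power (%) for PFS at HR 1.75 with 30-month drop-out, when some measurements carry gross error:

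| Error | Split | Linear Cox | Rank |
|---|---|---|---|
| None | 43.1 | 62.5 | 59.9 |
| 3% of patients, SD 6 | 40.9 | 47.8 | 55.0 |
| 7%, SD 6 | 38.2 | 34.5 | 49.0 |
| 7%, SD 3 | 39.6 | 46.8 | 52.2 |
| 15%, SD 3 | 35.2 | 35.1 | 43.9 |

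Rank leads the split by 9 to 14 points in all four error settings. Linear Cox runs from 4 points below the split to 7 above. The error rates are assumed, but the plan gives two routes to such error. Section 7.1: "A region-of-interest (ROI) will be manually drawn in the target lesion". Section 5.5, if the target becomes inevaluable: "an alternate lesion (evaluable baseline MR whenever possible, and adjacent to original target lesion) will be selected for analysis".

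**The case against.** The strongest reply is that nothing here is an error. The split is fixed in advance, keeps type I error near 5%, resists outliers and suits Kaplan-Meier display. The endpoints are secondary, unpowered and unadjusted for multiplicity. The headline effects (HR 1.75, OR 3 per SD) are assumed and large. At HR 1.25 both tests usually fail, and with heterogeneity even the rank test has only 37% to 45% power at HR 1.75. All of that stands. It limits the size of the gain but does not reverse it.

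The PFS model may also be generous. Part B follows Part A within one 24-month accrual period, and disease is assessed only every 6 to 12 weeks (Section 5.7). With censoring at 6 to 15 months (assumed) and 12-weekly assessment there are about 16 events, and power is 36% v 51% at HR 1.75, 23% v 31% at 1.5 and 11% v 13% at 1.25. Rank still leads.

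The comparison with the tissue analyses should not be overstated. Section 7.8.3 also groups the immunohistochemistry scores, and Spearman's coefficient does not handle censored PFS. The passages do not contradict each other; the plan simply already accepts rank methods for this biomarker.

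Finally, a rank score test gives no estimate of effect size for PFS. That estimate must come from a supportive Cox model that is itself sensitive to outliers. This is a real limit of the remedy.

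**Conclusion.** The concern holds. The plan tests a graded question with a two-group comparison. If the association is graded, a rank analysis of the same 30 patients detects it more often: by about 15 to 18 points for PFS at HR 1.75 per SD with 17 to 24 events, and by about 16 to 17 points for response and clinical benefit at OR 3 per SD. The gain falls to 10 to 13 points with unmodelled heterogeneity and to about 4 points at HR 1.25. If the truth is a step at the population median there is no gain.

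The direction is secure for graded effects. The sizes rest on assumed effects, rates, event counts and error rates, because the documents give none for these endpoints. The Part B primary endpoint is not touched. This is an inexpensive improvement that should be made, not a flaw that invalidates the study.

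**What to change.** In Section 7.8.3, make a rank-based analysis of the undivided percent change the main analysis, fixed before outcomes are analysed and whatever the event count:

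- **PFS:** two-sided Cox score test on ranked percent change.
- **Response and clinical benefit:** Mann-Whitney test of percent change by outcome, reported with the concordance probability (the chance that a patient with the outcome had the larger decline) and its 95% CI.
- **Supportive only:** Cox hazard ratio with 95% CI per 10 percentage points of change, with a plot to check linearity and outlying values.
- **Illustration:** keep the median-split Kaplan-Meier curves.

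No new data or patients are needed, and ranks give the same answer on the percent or log-ratio scale. Because Section 7.8.3 is protocol text, Section 8.4 requires an amendment with protocol review committee and IRB approval.

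The statistical price is about 3 points against linear Cox when PFS data are clean (62.5% v 59.9%). Against the split, if the truth is a step at the population median, it is 1 to 2 points for PFS and about 1 to 6 for the binary outcomes, depending on the rates. If the step falls exactly at this sample's median, a value unknown until the data are in, the price is 13 to 16 points. The documents give no reason to expect either step.

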5.7 Every 6-12 weeks (Part B Only)

Patients will undergo standard disease assessments including standard staging scan every 6-12 weeks per standard of care or per protocol on therapeutic clinical trial. Patients will be followed discontinuation of PI3K/mTOR pathway inhibitor therapy, due to disease progression, unacceptable toxicity, or patient/physician decision to discontinue therapy.

Table 2: Schedule of Study Procedures and Assessments

Period/ Procedure	Screening (28 Days)	Cycle 1 Day 1	Day 21 (+/- 14 days)	Day 28 (+/- 14 days)	Every 6-12 Weeks	Disease Progression
Informed consent	x					
Baseline conditions	х					
AE assessment	х		Х			
Concomitant medications	х		х			
Physical exam	Х					
Vital signs	Х		Х			
Medical history/ Demographics	х					
Tumor Assessment by Standard Scans (within 3 months of C1D1)	Х				X (Part B only)	
Performance status	х					
CBC w/ Diff	х					
Blood chemistry	х					
HP C- 13/metabolic MRI	х		X (Part B only)			
ECG/EKG	х					
		Pai	rt B Only			•
PI3K/mTOR Pathway Inhibitor						
Tumor biopsy (Optional)	Х			х		

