7.3 Sample Size Determination

In Part A of the study, 50 subjects with advanced solid tumor malignancies and at least one metastatic liver or intra-abdominal lesion will undergo hyperpolarized C-13

pyruvate/metabolic MR imaging. The coil arrays will undergo iterative adjustment in geometry and design to optimize the signal-to-noise ratio of intra-tumoral HP lactate/pyruvate.

In Part B of the study, the sample size of 30 evaluable patients is based upon the primary endpoint of this portion of the study, the mean percent change from baseline in peak intratumoral lactate/pyruvate ratio in the target metastatic lesion after initiation of treatment with PI3K/mTOR pathway inhibitor. Assuming the intra-tumoral lactate/pyruvate ratio is 0.80 at baseline and the expected ratio at day 14 is 0.45 (e.g. a 35% decline), based on prior preclinical studies, then a sample size 30 will have > 85% power to detect the significance of the change in signal under paired t-tests with type I error of 5%.

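### Objective response is tested only as responder yes/no by chi-squared in about 15 v 15 patients; an exact test and an added ordered-response analysis would use the same scans better

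*Combined protocol and SAP*

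**What the plan says.** Section 7.3 sets Part B at "the sample size of 30 evaluable patients". For clinical outcomes, section 7.8.3 says that "the cohort will be dichotomized by the median percent change", which gives about 15 v 15. It continues: "The objective response rate by RECIST 1.1 criteria and clinical benefit rate (response or stable disease for > 24 weeks) will be compared". The two halves are the groups compared, and chi-squared is the only test named for these two rates. For timing of progression: "The log rank test will be used to compare the radiographic progression-free survival between the two groups".

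Section 2.2 names objective response, clinical benefit and PFS as examples of the outcomes of interest. The endpoint list in 7.2 names clinical benefit and PFS but not objective response.

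The raw material for a graded outcome is already planned. Section 5.7 says: "Patients will undergo standard disease assessments including standard staging scan every 6-12 weeks per standard of care or per protocol on therapeutic clinical trial". Section 7.8.3 already uses Spearman correlation, but only for the imaging marker against continuous tissue markers.

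The documents give no expected response rate, power or small-count alternative for the response comparison. The 5% level appears only in the primary power statement in 7.3, without sidedness, and 7.8.3 applies no multiplicity adjustment.

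**The concern.** RECIST response cuts a graded measure: change in summed lesion size, reported as the ordered categories CR, PR, SD and PD. Reducing it to responder yes/no puts stable disease and progression in the same cell. Section 1.2 reports that preclinical falls in the lactate/pyruvate signal went with later stabilisation of growth, so the contrast between SD and PD is one that the marker might be expected to track.

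The yes/no form also makes a sparse table likely. In 15 v 15 patients, few responders would leave the test unable, or barely able, to show an association even if the marker separated responders perfectly. A non-significant result would then say little either way. This loss is on the outcome side and would remain if the median split of the imaging change were dropped.

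**Working it through.** **Inputs.** N = 30 (7.3); median split, so 15 v 15 (7.8.3); chi-squared (7.8.3). Two-sided 0.05 is an assumption carried over from the primary analysis. The plan has no figure of its own for this comparison to reproduce.

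**1. Smallest attainable p-value.** Put all r responders in one group. Without continuity correction,

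chi-squared = 30 × (15r)² / [15 × 15 × r × (30 − r)] = 30r / (30 − r).

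The two-sided Fisher p-value for r v 0 is 2 × C(15,r) / C(30,r).

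| Split | Chi-squared | p, uncorrected | p, Yates | p, Fisher |
|---|---|---|---|---|
| 2 v 0 | 60/28 = 2.14 | 0.143 | 0.464 | 0.483 |
| 3 v 0 | 90/27 = 3.33 | 0.068 | 0.224 | 2 × 455/4,060 = 0.224 |
| 4 v 0 | 120/26 = 4.62 | 0.032 | 0.107 | 2 × 1,365/27,405 = 0.0996 |
| 5 v 0 | 150/25 = 6.00 | 0.014 | 0.0500 | 2 × 3,003/142,506 = 0.042 |

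The 5% critical value is 3.84, so 3 or fewer responders can never reach it. With 4, only a perfect split does, and only under the uncorrected test. For 3 responders the limit holds at every N from 30 down to 22. It first fails at N = 21 (10 v 11, p = 0.0497).

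**2. Sparse cells.** Expected responders per group are 15r/30 = r/2, which is below 5 whenever r < 10.

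**3. How likely 3 or fewer responders is.** Binomial P(X ≤ 3), n = 30, at assumed response rates:

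| Response rate | 5% | 10% | 15% | 20% |
|---|---|---|---|---|
| P(X ≤ 3) | 94% | 65% | 32% | 12% |

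**4. Power by simulation.** All of these are assumptions: bivariate normal ratio change and size change, correlation 0.5, responders being the patients with the most shrinkage, 30% PD, n = 30, two-sided 5%. With 2,000 to 4,000 trials per setting, repeat runs agree within about 3 points.

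| Analysis | Power |
|---|---|
| Planned median split v response, chi-squared (response rate 10/20/30%) | about 14/32/42% |
| Unsplit ratio change v response, Mann-Whitney (10/20/30%) | about 30/45/54% |
| Planned median split v clinical benefit, chi-squared (50% rate) | about 42% |
| Unsplit ratio change v clinical benefit, Mann-Whitney (30-50% rate) | about 53-58% |
| Ratio change v ordered response, Spearman | about 66-71% |

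The outcome-side gain over unsplit binary response runs from 71 − 54 = 17 to 66 − 30 = 36 points. Over unsplit clinical benefit it is roughly 10 to 18 points. At zero correlation the Spearman tests rejected in about 5% of trials.

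**The case against.** **Other outcomes are planned.** A reader might infer that the whole imaging-outcome analysis rests on responder status. It does not. Clinical benefit uses a different cut that counts durable stable disease, and PFS uses the timing of progression. This stands. What is missing is ordered response and degree of shrinkage.

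**The gain is easily overstated.** Setting the ordered analysis against the planned response test alone gives 22 to 64 points (correlations 0.4-0.6, response rates 10-30%). Much of that comes from removing the median split, which is a separate matter, and it leaves clinical benefit out. The comparisons that isolate the outcome are the smaller ones above.

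**The limit is conditional.** A reader might infer that the response test cannot succeed. The documents give no response rate. At an assumed 20%, 3 or fewer responders occurs only 12% of the time, and the limit says nothing about clinical benefit or PFS unless those counts are also very small.

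**The scans will be noisy.** Baseline staging may precede the baseline MR by up to 12 weeks (5.1), follow-up intervals vary, and tumour types and drugs are mixed. For continuous size change, if its reliability is 0.8 or 0.6 (assumed), Spearman power falls from about 77% to about 67% or 53%. Binary response shares this noise, but the absolute powers are optimistic.

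**Objective response is a named outcome.** Section 2.2 names it, so testing it is not an error. This also stands: there is no need to demote it, and an added analysis is enough.

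**Conclusion.** The point holds as an inexpensive improvement to a secondary, unadjusted analysis. Two parts rest only on the plan's design and a two-sided 5% level: with 3 or fewer responders the response comparison cannot reach significance, and chi-squared can differ materially from the exact test in tables this sparse (0.032 against 0.10 at 4 v 0). How often this would bite depends on a response rate that the documents do not give; over assumed rates of 5 to 20% the chance runs from 94% down to 12%.

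The power gain from ordered response, about 17 to 36 points over unsplit binary response and roughly 10 to 18 over unsplit clinical benefit, also depends on the assumed correlation of 0.5, normality and 30% PD. The documents do not support reading this as a flaw in the primary endpoint, the safety analysis or the sample size.

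**What to change.** In 7.8.3:

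- Keep objective response and clinical benefit as named outcomes. Report each group's proportion with an exact confidence interval, and replace chi-squared with Fisher's exact test when any expected count is below 5.
- Add a pre-specified Spearman correlation, with 95% confidence interval, between percent change in lactate/pyruvate ratio and RECIST 1.1 best overall response kept in order (CR > PR > SD > PD).
- Optionally support it with best percent change in the sum of target-lesion diameters, ranking as worst any patient who progresses by new lesions or before a post-baseline measurement.

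This needs wording and a little analysis time. It needs no new scans or patients, since assigning RECIST response already requires the measurements and categories. The price is one more unadjusted secondary analysis, a more conservative test for the sparse tables, and some noise from variable scan timing.

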5.3 Tumor Biopsy (Part B only; optional)

Patients enrolled in Part B will undergo an optional core needle tumor biopsy of the preselected target lesion following completion of baseline metabolic MR scan but prior to initiation of PI3K/mTOR pathway inhibitor. The fresh biopsy sample will be delivered to the [name] lab and will be analyzed for markers of PI3K/mTOR pathway activation, including phosphorylated S6 and Akt, as well as markers of glycolytic activity including LDH expression. When sufficient tissue is available, expression level of MCT1 and MCT 4 (major lactate transporters) will be measured

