5.6 Repeat Tumor Biopsy (Part B Only; Optional)

Patients will undergo optional repeat core needle tumor biopsy following completion of the second MR scan. When possible, patients should remain on PI3K/mTOR pathway inhibitor through the time of the follow up biopsy. The same target lesion will be selected as that biopsied at baseline prior to study initiation whenever possible. In the event that the original target lesion is no longer accessible for repeat tumor biopsy, an alternative metastatic lesion will be selected. Whenever possible, this alternate lesion should be evaluable by metabolic MR imaging.

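### Merging the ordered immunohistochemistry score into two groups costs the exploratory pS6, pAkt, LDHA and MCT1/4 analyses some power; a rank correlation on the ungrouped score would avoid this (low priority)

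*Combined protocol and SAP*

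**What the plan says.** Section 7.8.3 relates the HP imaging markers to biopsy tissue in two ways.

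- When both variables are continuous, with LDHA activity as the example, Spearman's "rank correlation coefficient will be used to investigate a possible correlation between them".
- If the tissue outcome is categorical, for which the plan gives the example "immunohistochemistry score 0-1+ vs 2-3+ for pS6, pAkt, LDHA, and MCT 1/4 expression", then "the HP biomarker distributions will be compared between the two categories using the Mann-Whitney test".

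No analysis that uses the order of the score levels is described, and no reason is given for the cut. The same section makes no multiplicity adjustment for secondary and exploratory endpoints.

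Section 7.2 lists the endpoint as exploratory: "Association between HP peak lactate/pyruvate signal with immunohistochemical expression level of markers of PI3K/mTOR and glycolytic pathway". The tissue comes from optional procedures. Section 5.3 states "Patients enrolled in Part B will undergo an optional core needle tumor biopsy", and section 5.6 states "Patients will undergo optional repeat core needle tumor biopsy following completion of the second MR scan". Section 5.3 also limits MCT1 and MCT4 to cases with enough tissue. Part B has 30 patients (section 3.2), expected biopsy uptake is not stated, and section 7.8.1 leaves missing values missing.

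**The concern.** The endpoint concerns the level of marker expression, but the named test sees only low against high. A tumour scored 2+ is treated like one scored 3+, and 0 like 1+. Spearman's coefficient handles a tied, ordered score directly and already stands in the same paragraph.

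The study asks whether the HP signal tracks PI3K/mTOR pathway activity. The direct tissue readouts of that pathway are pS6 and pAkt, and in section 7.8.3 they appear only under the merged comparison. With few biopsies, a true association is more likely to be missed. If most tumours score 2+ or 3+, the low group may be nearly empty. A Mann-Whitney p-value also gives no correlation estimate to set beside the one for LDHA activity.

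**Working it through.** **No figure to reproduce.** The plan states no power, effect size or number of biopsies for this analysis. Its only power statement (section 7.3) concerns the Part B primary endpoint and does not bear on this point.

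**Inputs from the documents:** the example cut, the Mann-Whitney test, Spearman for continuous markers, optional biopsy, and at most 30 patients.

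**Assumed inputs:** four levels (inferred from the notation); one HP value and one score per patient; 12, 20 or 30 biopsied patients; a latent correlation of 0.5 between HP ratio and marker; two-sided 5%. Three score spreads over 0/1+/2+/3+ are used: even (25% each), U-shaped (40/10/10/40%) and skewed (5/15/30/50%).

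**Step 1: large-sample efficiency.** Let level k have proportion p, mean latent value μ and mid-rank m (cumulative proportion minus p/2). Let q be the proportion scored 2+ or 3+.

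- Four levels: c4 = Σ p μ (m − 0.5) / √[Σ p (m − 0.5)²]
- Two groups: c2 = (Σ p μ over 2+ and 3+) / √[q(1 − q)]
- Relative efficiency of the split = (c2/c4)²

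Even scores: μ = ±0.325 and ±1.271; m − 0.5 = ±0.125 and ±0.375.

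- c4 = 2 × 0.25 × (1.271 × 0.375 + 0.325 × 0.125) / √0.078125 = 0.2586 / 0.2795 = 0.925
- c2 = 0.25 × (0.325 + 1.271) / 0.5 = 0.798
- Efficiency = (0.798 / 0.925)² = 0.744

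So 20 biopsied patients are worth about 0.744 × 20 = 14.9. The same formula gives 0.850 for U-shaped scores (17.0 patients) and 0.636 for skewed scores (12.7 patients). If the HP ratio is instead linear in the score itself, the efficiencies are 0.80 (even), 0.92 (U-shaped) and 0.757 (skewed).

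**Step 2: power at small numbers.** I simulated 60,000 trials per cell. Mann-Whitney on two groups is, apart from its reference distribution, a Spearman test on a two-level score. Both scores were therefore tested with the same Spearman t approximation, so that type I error is comparable: 4.9-5.3% for four levels; 4.9-5.4% for two groups with even and U-shaped scores; 4.1-5.0% for two groups with skewed scores.

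| Scores | n | Two groups | Four levels | Loss (points) |
|---|---|---|---|---|
| U-shaped | 12 | 25.3% | 29.1% | 3.8 |
| U-shaped | 20 | 42.1% | 48.1% | 6.0 |
| U-shaped | 30 | 60.1% | 67.3% | 7.2 |
| Even | 12 | 25.0% | 32.3% | 7.3 |
| Even | 20 | 42.3% | 53.6% | 11.3 |
| Even | 30 | 59.5% | 73.0% | 13.5 |
| Skewed | 12 | 17.8% | 29.3% | 11.5 |
| Skewed | 20 | 31.0% | 48.8% | 17.8 |
| Skewed | 30 | 46.3% | 68.2% | 21.9 |

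**Step 3: why comparable type I error matters.** At n = 12 with even scores, a continuity-corrected normal-approximation Mann-Whitney test has type I error of 3.3% and power of 18.5%. Set against 32.3%, that suggests a loss of 13.8 points. Of this, 25.0 − 18.5 = 6.5 points come from the conservative approximation and 7.3 from merging.

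**Step 4: sparse groups.** With skewed scores, 20% of tumours fall in 0-1+. For 12 biopsied patients, the chance of at most one in that group is 0.8¹² + 12 × 0.2 × 0.8¹¹ = 0.069 + 0.206 = 0.275.

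**The case against.** The strongest case against is that nothing rests on this analysis. It is exploratory, the biopsies are optional and no power is claimed. The better method does not rescue it: four-level power is still only about 29-32% at n = 12 and 48-54% at n = 20. This stands, and it sets the priority.

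The cut is also an example under a conditional clause, not a fixed rule, and Mann-Whitney keeps the full ranking of the HP marker. Both are true. But no other analysis of these markers is given, and an example leaves the choice of cut open until the data are seen.

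A reader might infer more than the documents support:

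- *That no other analysis links imaging to tissue.* Spearman is planned for continuous LDHA activity. The statement holds only for pS6, pAkt and the other markers read by IHC.
- *That most of the power is lost.* The documents give no score distribution. The loss is small with U-shaped scores, moderate with even scores and large only with skewed ones.
- *That the test is wrong.* It is valid for two groups; the loss comes from merging.
- *That four levels are already on record.* The documents do not say how scores are recorded.
- *That fewer than 30 patients will certainly be biopsied.* Thirty is the ceiling and uptake is unstated. Biopsies are offered at two time points, and the plan does not say which enters the association.

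**Conclusion.** The point holds as a minor matter of efficiency. Merging lost power in every case tried: about 4 to 7 points with U-shaped scores, 7 to 14 with even scores and 12 to 22 with skewed scores, for 12 to 30 biopsied patients. These figures rest on the assumed correlation of 0.5, the assumed spreads, the inferred four levels and one observation per patient. At n = 12 with skewed scores, a little of the gap still reflects the lower type I error of the two-group test (4.1% against 5.1%). The Part B primary result is not affected. Priority: consider.

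**What to change.** In section 7.8.3, state that where IHC is scored on ordered levels, the association is estimated by Spearman's rank correlation (or Kendall's tau-b) between the HP ratio and the ungrouped 0 to 3+ score, with a 95% confidence interval. Keep the 0-1+ against 2-3+ split as a descriptive plot or table.

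The cost is one sentence, using a method already in that paragraph. It adds no procedure or patient burden, provided the score is recorded ungrouped. The sponsor should confirm this and, if necessary, have the case report form record the individual level.
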